### **Visit 10: Extension Period (Week 40)**

Procedures that will be performed at Visit 10 (Week 40) include:

- Record concomitant medication(s);
- Assess vital signs;
- Obtain fasting blood sample for the following assessments:
  - Serum chemistry (see Appendix A for a complete list of analytes);
  - Hematology (see Appendix A for a complete list of analytes);

- Coagulation (see Appendix A for a complete list of analytes); and
- Lipid parameters (see Appendix A for a complete list of analytes);
- Obtain urine sample for urinalysis (see Appendix A for a complete list of analytes);
- Provide TLC counseling (see Section 8.5.1);
- Dispense study drug via the IRT system and provide instructions for proper use;
- Collect study drug and assess study drug accountability;
- Assess and record AEs; and
- Schedule Visit 11 (52 weeks  $\pm$ 7 days from Visit 4).

### Visit 11: Extension Period (Week 52) or Early Termination Visit

Procedures that will be performed at Visit 11 (Week 52) include:

- Record concomitant medication(s);
- Assess vital signs, weight, and waist circumference;
- Perform 12-lead ECG;
- Perform physical examination;
- Obtain fasting blood sample for the following assessments:
  - Serum chemistry (see Appendix A for a complete list of analytes);
  - Hematology (see Appendix A for a complete list of analytes);
  - Coagulation (see Appendix A for a complete list of analytes);
  - Lipid parameters (see Appendix A for a complete list of analytes);  
■ [REDACTED]  
■ [REDACTED]  
■ [REDACTED]  
■ [REDACTED]
- Obtain urine sample for urinalysis (see Appendix A for a complete list of analytes) and urine pregnancy test (WOCBP only);
- Provide TLC counseling (see Section 8.5.1);
- Collect study drug and assess study drug accountability; and
- Assess and record AEs.

## 6.4 COMPLIANCE WITH THE PROTOCOL

The Investigator must agree to implement the study protocol as written and adhere to the guidelines given in the "Investigator's Statement," which will be signed by the Investigator prior to the start of the study. The study will be performed in accordance with Declaration

of Helsinki, International Council for Harmonisation (ICH) Good Clinical Practice (GCP) guidelines, local laws, and other applicable guidance documents. Sites in the United States will also comply with the Health Insurance Portability and Accountability Act (HIPAA) and Food and Drug Administration (FDA) GCP regulations (21 Code of Federal Regulations [CFR] Parts 11, 50, 54, 56, and 312).

Protocol noncompliance must be reported to [REDACTED] and Kowa Research Institute, Inc. (KRI). Each deviation and the reason for its occurrence must be documented. Kowa Research Institute, Inc. retains the right to require the withdrawal of any patient who violates the protocol.

## 6.5 TERMINATION OF THE STUDY

### 6.5.1 Site Termination

If it becomes apparent that patient enrollment is unsatisfactory with respect to quality or quantity, or data recording is inaccurate or incomplete on a chronic basis, KRI has the right to terminate the study at an investigational site and remove all study materials from the investigational site. A written statement will be provided to the Investigator, the Institutional Review Board (IRB)/Ethics Committee (EC), and regulatory authorities, if required. In the event of any serious or non-serious AE(s) having occurred at a site, all documentation relating to the event(s) must be obtained.

### 6.5.2 Study Termination

If, in the opinion of KRI, the clinical observations in the study suggest that it may be unwise to continue, the study may be terminated. In addition, KRI may terminate the study at any time.

## 6.6 LABORATORY ALERT RELATED TO HIGH TRIGLYCERIDES

Sites will receive an alert for any reported TG level >2000 mg/dL (22.60 mmol/L) during the study. In order to maintain the study blind during the placebo-controlled 12-week Efficacy Period, sites may receive a sham alert. A sham alert is an alert which will be sent to a site for randomly selected patients who do not actually meet the alert criteria for TG levels >2000 mg/dL (22.60 mmol/L). These alerts will be programmed to occur in patients assigned to K-877, at the expected (low) frequency that they would occur in the placebo population, and will be indistinguishable from “true” alerts. Investigators are expected to respond to every alert (see Section 5.2.2.3).

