#### 5.2.2.3 *Triglyceride Elevations*

For alerts due to fasting TG levels  $>2000$  mg/dL (22.60 mmol/L), the patient should return to the site within 1 week for clinical and laboratory assessments. Patients should be assessed for potential signs or symptoms of pancreatitis (including measurements of serum amylase and lipase), and a repeat assessment of fasting TG will be obtained. For patients with asymptomatic elevations of TG, compliance with study drug and lifestyle recommendations should be assessed and reinforced. Patients should be closely followed for the emergence of signs and symptoms of pancreatitis until TG levels are  $<2000$  mg/dL (22.60 mmol/L). If 2 consecutive alerts for a patient are sent due to elevated TG levels  $>2000$  mg/dL (22.60 mmol/L), the Investigator may contact the Medical Monitor to discuss study drug discontinuation and further monitoring.

To maintain the integrity of the blind, TG values from post-randomization blood samples obtained prior to Visit 8 (Week 16), run by the central laboratory, will not be communicated to the sites (see Section 6.6).

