## **9.0 ADVERSE EVENTS**

### **9.1 ADVERSE EVENT DEFINITION**

An AE is any untoward medical occurrence in a patient administered a pharmaceutical product and which does not necessarily have a causal relationship with the pharmaceutical product. An AE can, therefore, be any unfavorable and unintended sign, symptom, or disease temporally associated with the use of a medicinal product, whether or not related to the medicinal product. Any worsening of the patient's disease under study or other medical conditions will also be considered to be an AE, unless it is within the normal range of disease fluctuation for that patient.

Clinically meaningful (for a given patient) changes in physical examination findings and abnormal objective test findings (e.g., clinical laboratory tests, ECGs) will also be recorded as AEs. The criteria for determining whether an abnormal objective test finding will be reported as an AE are as follows:

1. Test result is associated with accompanying symptoms, and/or;
2. Test result requires additional diagnostic testing or medical/surgical intervention, and/or;
3. Test result leads to a change in study drug dosing or discontinuation from the study, significant additional concomitant drug treatment or other therapy, and/or;
4. Test result leads to any of the outcomes included in the definition of an SAE.

Merely repeating a test, in the absence of any of the above conditions, does not meet condition number 2 above for reporting as an AE.

Any abnormal test result that is determined to be an error does not require reporting as an AE.

A treatment-emergent AE (TEAE) is defined as an AE that begins after the start of study drug or an event that begins before the start of the study drug and worsens in intensity after starting treatment with the study drug.

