## **15.0 APPENDICES**

### **APPENDIX A: CLINICAL LABORATORY PARAMETERS**

#### **Chemistry**

Sodium  
Chloride  
Potassium  
Bicarbonate  
Calcium  
Inorganic phosphorus  
Blood urea nitrogen  
Creatinine  
Estimated glomerular filtration rate (eGFR)  
Uric acid

Alanine aminotransferase (ALT)  
Aspartate aminotransferase (AST)  
Alkaline phosphatase  
Gamma-glutamyl transpeptidase (GGT)  
Total bilirubin  
Direct bilirubin  
Albumin  
Total protein

Lipase (Visits 1 and 4 only)  
Amylase (Visits 1 and 4 only)

Creatine kinase (CK)  
Lactate dehydrogenase

Glucose  
Insulin (Visits 4, 7, 9, 10, and 11 only)  
Glycosylated hemoglobin (HbA1c) (Visits 1, 4, 7, 9, 10, and 11 only)  
Glycated albumin (Visits 4, 7, 9, 10, and 11 only)  
Homeostasis model assessment for insulin resistance (Visits 4, 7, 9, 10, and 11 only)  
Homeostasis model assessment for beta-cell function (Visits 4, 7, 9, 10, and 11 only)  
Quantitative insulin sensitivity check index (Visits 4, 7, 9, 10, and 11 only)  
Homocysteine

[REDACTED]  
[REDACTED]

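### Sham high-TG alerts are programmed only in the K-877 arm, and the supplied text plans no table separating the TG-elevation AEs they may prompt during the 12-week period

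*Protocol*

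**What the plan says.** - **Who gets a sham alert.** Under protocol 6.6, during the 12-week Efficacy Period a sham alert concerns "randomly selected patients who do not actually meet the alert criteria" for TG above 2000 mg/dL. On allocation: "These alerts will be programmed to occur in patients assigned to K-877, at the expected (low) frequency" that true alerts would have on placebo. No sham alerts are described for placebo patients, so I read this as K-877 only, although the protocol does not use that word. Shams look the same as true alerts, and sites must respond to all of them.
- **What the site does.** Section 5.2.2.3 asks for a return visit within 1 week, an assessment for pancreatitis ("including measurements of serum amylase and lipase") and a repeat fasting TG. Appendix A otherwise schedules amylase and lipase only at Visits 1 and 4.
- **What the site can see.** TG values from samples taken after randomization and before Week 16, "run by the central laboratory, will not be communicated to the sites" (5.2.2.3). Section 6.1 discourages local lipid panels.
- **When a test result is an AE.** Section 9.1 applies to findings that are clinically meaningful for the patient. One criterion is: "Test result requires additional diagnostic testing or medical/surgical intervention". Merely repeating a test does not meet it. There is one exemption for false results: "Any abnormal test result that is determined to be an error does not require reporting as an AE". Worsening of the disease under study is an AE "unless it is within the normal range of disease fluctuation for that patient".
- **How AEs are tabulated.** Section 11.6 summarizes treatment-emergent AEs by system organ class and preferred term, for the 12-week period among others. It makes no distinction by type of alert.
- **The SAP.** The supplied document is a post-lock addendum about zero laboratory values. It does not mention alerts or AE tables. The body of SAP version 2.0 was not supplied.

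**The concern.** Sham alerts are a legitimate blinding device. The difficulty is that they act on one arm and can feed a table that compares arms. A site that follows the rules may record a TG-elevation AE after a sham alert. It has no means of learning that the alert was false, so the exemption for erroneous results is out of its reach. The entry then counts as a K-877 event in the only placebo-controlled AE comparison.

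Placebo patients have true alerts at about the rate the shams are set to match. The main consequence is therefore to hide a K-877 advantage on this term. A reader of the AE table alone could not see which entries had a central TG above 2000 mg/dL behind them. In a trial of a TG-lowering drug, that is a term readers will look for.

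**Working it through.** **Does the path exist?**

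1. Sham alerts go to K-877 patients (6.6), and every alert must be acted on (6.6).
2. The response includes amylase and lipase (5.2.2.3). Neither is scheduled after Visit 4 (Appendix A), so the response is more than repeating a test.
3. Additional diagnostic testing is a listed AE criterion (9.1). Recording remains a judgment, because 9.1 also asks for clinical meaning and exempts normal disease fluctuation.
4. The site cannot classify the alert as an error (5.2.2.3, 6.1, 6.6).
5. The planned table does not separate such AEs (11.6).

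So a sham-prompted AE is possible, but not certain.

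**How large could it be?** The plan gives no alert frequency, so there is no figure to reproduce. The arm sizes check: 630 × 2/3 = 420 on K-877 and 630 × 1/3 = 210 on placebo.

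All other inputs are my assumptions:
- p, the 12-week alert rate per placebo patient: 0.5% to 2%.
- Sham rate on K-877: equal to p.
- q, the true alert rate on K-877: 0.2p.
- f, the share of alerts recorded as a TG-elevation AE: 10% to 50%, the same for true and sham alerts because sites cannot tell them apart.

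Expected sham-prompted AEs = 420 × p × f:

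| p | Sham alerts (420p) | f = 10% | f = 25% | f = 50% |
|---|---|---|---|---|
| 0.5% | 2.1 | 0.21 | 0.53 | 1.05 |
| 1% | 4.2 | 0.42 | 1.05 | 2.10 |
| 2% | 8.4 | 0.84 | 2.10 | 4.20 |

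The chance of at least one is 1 − (1 − pf)^420. It runs from 0.19 (p = 0.5%, f = 10%) to 0.985 (p = 2%, f = 50%). In the middle case (p = 1%, f = 25%) it is 1 − 0.9975^420 = 0.65.

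AEs from true alerts, for comparison:
- Placebo, 210 × p × f: 0.11 to 2.10 (middle 0.53).
- K-877, 420 × 0.2p × f: 0.04 to 0.84 (middle 0.21).

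Middle case as rates:
- From true alerts only: K-877 0.2% × 25% = 0.05%; placebo 1% × 25% = 0.25%; difference −0.20 points.
- As tabulated: K-877 (1% + 0.2%) × 25% = 0.30%; placebo 0.25%; difference +0.05 points.
- Shift against K-877 = pf = 0.25 points. Over the whole range it is 0.05 to 1.0 points.

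**Sensitivity to how 6.6 is read and to the assumptions.**
- If shams only top K-877 up to the placebo rate, the sham rate is p − q = 0.8p. Expected sham-prompted AEs are then 0.17 to 3.36 (middle 0.84), and the tabulated difference is 0.
- If shams match the placebo count instead of the rate, the entries in the table halve.
- If f is near zero, so is the effect. At p = 3% and f = 50% the expectation would be 420 × 0.03 × 0.5 = 6.3.

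**The case against.** The strongest case against has five parts.

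- **The gap may already be filled.** Safety tables and listings normally sit in the SAP, and version 2.0 was not supplied. This stands, and it makes the point conditional. Section 12.9 also requires study documentation to be retained in general terms, which should cover the record of sham alerts. This stands too: no new retention duty is needed, only a statement of where the record is held until unblinding.
- **A sham alert does not mean a normal TG.** A reader might infer that these AEs describe elevations that never happened. The documents do not support that. Section 6.6 says only that the alert threshold was not met, and patients entered with TG from 500 to below 2000 mg/dL. For example, a patient whose TG rose from 700 to 1600 mg/dL could receive a sham alert and have a real rise. This stands, and it is why the table should show the actual value as well as the classification.
- **The path to an AE is uncertain.** For asymptomatic elevations, 5.2.2.3 asks for reinforcement of compliance and lifestyle advice and gives no AE instruction. The section on creatine kinase (5.2.2.2) does address AE reporting. This stands: f could be close to zero.
- **Every rate is assumed.** This stands. The change of sign in the middle case also needs shams added on top of true K-877 alerts.
- **No decision changes.** A reader who wants TG elevations by arm would use the central laboratory data, and the TG summaries in 11.5.2 include the maximum at each scheduled visit. This is right about efficacy. It does not answer the narrower point, because those summaries do not show which AEs had a TG above 2000 mg/dL behind them.

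**Conclusion.** The point holds as a minor safety-reporting improvement; its label is cheap improvement. Following the protocol as written can place a few alert-prompted TG-elevation AEs in the K-877 column with no central TG above 2000 mg/dL behind them, and the supplied text plans no table that separates them. The illustrative size is about 0 to 4 AEs among 420 patients, with about one in the middle case. It rests wholly on assumed values of p, q and f and on the reading that shams match the placebo rate.

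Two stronger inferences are tempting, and the documents support neither. One is that the shams manufacture a harm signal for K-877. At rates matched to placebo they mainly mask a benefit, and under the top-up reading the arms simply look equal. The other is that the trial's validity is at risk. The primary endpoint and the laboratory summaries use measured central values. Suspected pancreatitis is adjudicated blind (5.5), and the enzyme results are real. The information is also recoverable: after unblinding, the central TG value shows whether an alert was true or sham.

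**What to change.** Keep the sham allocation, and keep the all-events treatment-emergent AE table as the main table. No AE is removed.

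- **In 11.6, add:** For the 12-week Efficacy Period, one supplementary table will present, in both arms, TG-elevation AEs linked to an alert. They will be classified by whether the triggering central TG was above 2000 mg/dL, with the actual TG value shown.
- **Linkage rule.** A workable window runs from the date of the alert's sample to 14 days after the alert. This is a suggestion; 5.2.2.3 asks for the visit within 1 week.
- **In 6.6, add:** The record of sham alerts (patient, visit, date), retained under 12.9, will be held outside the blinded database until unblinding. This matters because the record reveals K-877 assignment.

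If SAP version 2.0 already provides this, a cross-reference is enough. The addendum reports that the database has been locked and unblinded, so the practical step now is the supplementary table, labelled as added after unblinding, provided the alert records are available.

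The cost is a small programming task. Linking by date will occasionally misclassify an AE, which is a further reason to leave the all-events table as the main one.

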## 7.0 INVESTIGATIONAL DRUG

## 7.1 DESCRIPTION OF STUDY DRUGS

Kowa Research Institute, Inc. will supply sufficient K-877 0.2 mg film-coated tablets and matching placebo to allow for completion of the study. The lot numbers of the study drug will be recorded in the final study report.

All K-877 and matching placebo tablets are [REDACTED] To ensure study blinding can be maintained, each tablet is indistinguishable by size, markings, or weight. Each K-877 tablet contains 0.2 mg of K-877; each K-877 and placebo tablet also contains the following excipients: [REDACTED]

Fenofibrate is supplied as a white to off-white bi-convex oblong tablet containing 145 mg fenofibrate, as well as the following excipients: anhydrous lactose, croscarmellose sodium, hypromellose, magnesium stearate, purified water, simethicone emulsion, sodium lauryl sulfate, polyvinyl alcohol, titanium dioxide, talc, soybean lecithin, and xanthan gum. To ensure study blinding can be maintained, each tablet will be over-encapsulated and backfilled with anhydrous lactose, and matching placebo capsules containing anhydrous lactose as a backfill will be manufactured by [REDACTED]

## 7.2 DRUG PACKAGING

Drug packaging will be completed by an

Study drugs will be packaged in clear polyvinyl chloride/aluminum foil blisters within a child-resistant sleeve. Patients will have approximately a 1-month supply of study drug in each blister card. Study drug will be labeled in accordance with Section 7.3. Patients will receive an adequate supply of study drug at each visit to ensure proper dosing can occur until the next scheduled study visit.

## 7.3 DRUG LABELING

Study drugs will be labeled according to country/state/province specific requirements. For example, the label will include the following information:

- Name and address of Sponsor (i.e., KRI);
- A study reference code (e.g., protocol number) allowing ID of the investigational site and Investigator;
- Blank space for patient ID;
- Blank space for site/Investigator ID;

- Route of administration, quantity of dosage units, and pharmacological form as appropriate;
- A code number that will allow appropriate blinded assignment of the correct clinical trial material kit via the randomization code;
- Lot number (as required);
- Directions for use;
- The statement “Caution - New Drug - Limited by Federal (United States) Law to Investigational Use”;
- The statement “Keep out of reach of children”;
- The storage conditions; and
- Expiration date (as required).

#### **7.4 DRUG STORAGE**

K-877 0.2 mg tablets, fenofibrate 145 mg capsules, and matching placebos will be stored at controlled room temperatures of 20°C to 25°C (68°F to 77°F) in a secured area with access limited to the Investigator and the site staff. The permitted excursion temperature range is 15°C to 30°C (59°F to 86°F).

#### **7.5 DISPENSING AND ADMINISTRATION OF TREATMENT**

Study drugs will be dispensed to eligible patients beginning at Visit 4 (Day 1) after randomization via the IRT system and at Visit 5 (Week 4), Visit 6 (Week 8), Visit 7 (Week 12), Visit 8 (Week 16), Visit 9 (Week 28), and Visit 10 (Week 40). From Visit 4 (Day 1) to Visit 6 (Week 8), an approximately 1-month supply of blinded study drug will be dispensed to patients at each visit. Each patient will receive 1 blister card of K-877 0.2 mg or matching placebo. At Visit 7 (Week 12), an approximately 1-month supply of blinded study drug will be dispensed. Each patient will receive 1 blister card of K-877 0.2 mg or matching placebo, and 1 blister card of fenofibrate 145 mg or matching placebo. From Visit 8 (Week 16) to Visit 10 (Week 40), an approximately 3-month supply of blinded study drug will be dispensed at each visit. Each patient will receive 3 blister cards of K-877 0.2 mg or matching placebo, and 3 blister cards of fenofibrate 145 mg or matching placebo.

##### **7.5.1 Drug Administration**

Patients will receive an oral dose of K-877 0.2 mg or matching placebo twice daily starting at Visit 4 (Day 1) until Visit 7 (Week 12). Starting at Visit 7 (Week 12), patients will receive an oral dose of K-877 0.2 mg twice daily and placebo matching fenofibrate once daily, or fenofibrate 145 mg once daily and placebo matching K-877 twice daily. Patients may take study drug in a fed or fasted state (before or after meals); however, patients should be instructed that fed/fasted state and dosing time should remain consistent for all doses throughout the study. Study drug will be dispensed at Visit 4 (Day 1) through Visit 10

---

(Week 40). Patients will be instructed by the site to follow dosing instructions on the drug packaging and to return the remaining study drug at the next visit.

## **7.6 COMPLIANCE WITH PRESCRIBED STUDY DRUG DOSING REGIMEN**

Study drug or placebo will be dispensed in excess of the amount required between study visits. Patients will be instructed to return all unused study drug at the next visit. The patient will be asked whether there have been any problems with taking the medication, and the Investigator will record any significant departure from the dosing instructions (e.g., misuse or overdose) as a protocol deviation. A record of the number of tablets/capsules dispensed, taken, and returned for each patient must be documented on the Drug Accountability Log and eCRF. Compliance will be assessed from information recorded in the eCRF, including study drug count and the start and end date of therapy. Patients will be considered compliant if they have taken between 80% and 120% of the intended regimen.

During the treatment period, if compliance is not between 80% and 120%, inclusive, the patient will be counseled about the importance of compliance with the regimen. See Section 7.5.1 for study drug administration.

## **7.7 DRUG ACCOUNTABILITY**

Sites will be instructed to maintain drug accountability and retain all used, partially used, and unused study drug materials until the end of the study.

## **7.8 PROCEDURE FOR UNBLINDING**

As needed, the randomization code may be broken by the Investigator to manage an urgent medical event. If possible, the Medical Monitor will be contacted to discuss the case and ET assessments will be completed before the code is broken.

For each patient, the treatment group can be unblinded using the IRT system and the site's Emergency Unblinding IRT Code, provided with the site's study start-up materials. Using the Emergency Unblinding IRT Code, the Investigator or designee will be able to unblind a patient by following the instructions on [REDACTED]. When the unblinding is completed, the study's Medical Monitor, the Clinical Trial Manager, and designated KRI personnel will be notified that the unblinding has taken place.

If it becomes necessary to unblind treatment information during the study, the reason for unblinding must be documented in the eCRF. The Investigator must contact the Medical Monitor within one business day and explain the reason for the premature unblinding (e.g., unblinding due to a serious AE [SAE]). Patients whose treatment assignment is unblinded are no longer eligible to receive treatment. Patients unblinded during the 12-week Efficacy Period should complete the 12-week Efficacy Period. Patients who are unblinded in the 40-week Extension Period must be discontinued from the study after ET assessments are completed (see Section 6.3).

